8.1. Missing and Imputed Data

Every effort will be undertaken to fulfill all the requirements of the protocol concerning the collection of data. If participants refuse to return for data collection, but agree to continue in the study, questionnaire data and safety data will be collected over the telephone or at a home visit, if necessary.

The primary analysis will be performed on the ITT group. Those participants who withdraw or who are lost to follow up (LTFU) after enrollment will be included in the primary analysis using a last observation carried forward (LOCF) approach where the outcome at the most recent visit will be carried forward to all subsequent missing assessment times. Since all postbaseline efficacy assessments are first assessed at approximately Week 8, participants without an 8-week visit will have their baseline observation carried forward (BOCF) for the primary and secondary efficacy analyses. Analyses will also be performed on all available data with no imputations.

8.2. Hypothesis Testing

The treatment consists of 3 active caps and one Sham cap. Each active cap group will be compared to the same Sham group using 1 degree of freedom contrasts in general linear models analysis of covariance (ANCOVA). Comparisons will be adjusted for multiple comparisons to the same Sham group using Dunnett's correction.

The primary outcome is the change from baseline in hair count after 16 weeks of treatment with a cap. The null hypothesis is there is no difference in outcome between an active cap compared to a Sham cap, while the alternative hypothesis is there is a difference outcome between active compared Sham cap:

 H_{null} : $D_{active} = D_{Sham}$

 $H_{alternative} \text{: } D_{active} \neq D_{Sham}$

The null hypothesis will be rejected in favor of the alternative hypothesis for each active cap if the Dunnett's corrected p-value for the contrast ≤ 0.05 . Treatment superiority will be

demonstrated if the significant difference is in favor of the active cap (e.g., greater increase in hair count for the active cap. No comparisons between active caps will be performed.

Secondary outcomes will the same hypotheses testing process as the primary outcome, but with statistical methods appropriate for the type of endpoints to be tested. For example, continuous outcomes will be analysed by parametric methods, such as ANCOVA, while categorical outcomes will be analysed by non-parametric methods, such as Cochran-Mantel-Haenszel (CMH) test. Details of analyses by outcomes are provided in Section 10.

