5. SAMPLE SIZE CONSIDERATIONS

Prior hair growth studies, regardless of potential efficacy of the Sham device, showed the delta between active treatments and control treatments was consistently at around 15-22 hairs/cm² which appears to be the expected level of improvement. It is estimated that participants in the active group will have increases of 15 hairs/cm² by 16-weeks. Assumptions are 15 hair count difference between treatments, standard deviation (SD)=20, 10% drop-out rate, 5% alpha level, 90% power and 2-sided t-test. Based on these assumptions, the study requires a minimum of 40 evaluable participants per arm.

The study will accrue a maximum of 200 participants (50 per each Active Study Arm and 50 control participants) to target, after lost to follow-up, a minimum of 160 evaluable (40 per arm) participants.

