8. GENERAL CONSIDERATIONS FOR DATA ANALYSES

The purpose of the study is to collect data on the safety and effectiveness of *REVIAN* in participants with AGA. In general, for continuous variables, the sample size, mean, standard deviation, minimum and maximum will be presented. For categorical variables, the number and percentage in each category will be presented. All statistical analyses will be performed using SAS version 9.4 for PC. Unless otherwise specified, statistical significance will be determined using p ≤ 0.05 .

All outcomes will be provided in listings by participant and treatment group. In addition, some endpoints will be summarized in tables by treatment group.

Primary Efficacy Endpoint: The primary efficacy endpoint of this study is the change in hair count from baseline to 16-weeks following the initial application (CFB HC16).

Primary Safety Endpoint: The primary safety outcome will be determined by evaluating by the type, frequency, severity, and relatedness of adverse events through the 16-week period for all participants.

Secondary Efficacy Endpoints:

Change from Baseline Hair Count: Like the primary endpoint, change from baseline hair count, will also be assessed at 8 (CFB_HC08) and 26 (CFB_HC26) weeks.

Rate of Change in Hair Growth: The rate of change in hair growth at 8, 16, and 26 weeks will be calculated as a ratio of change from baseline to baseline.

Independent Physician's Global Assessment (iPGA): Two independent reviewers will assess overall hair growth from photographs, using PGA scores at weeks 8, 16 and 26. The PGA score hair growth as: -3=greatly decreased, -2=moderately decreased, -1=slightly decreased, 0=no change, 1=slightly increased, 2=moderately increased and 3=greatly increased. In the event the two independent reviewers do not agree, a third assessment will be made by the PI. The PI's score will superceed the two other independent reviewers' score.

Site Physician's Global Assessment (sPGA): The site investigator will assess overall hair growth using the PGA scores at weeks 8, 16 and 26.

Subjective Scalp Hair Growth Score (SHG): Beginning at Week 8, participants will complete a subjective hair growth questionnaire. The participants choose the answer that best fits the following statements:

- 1) Since the start of the study, I can see my bald spot getting smaller. (1="strongly agree" to 5="strongly disagree")

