10.2. Secondary Analyses

Secondary efficacy endpoints will be analysed as follows:

Change from Baseline Hair Count: the change from baseline hair count at 8 (CFB_HC08) and 26 (CFB_HC26) weeks will be analyzed in the same manner as the primary endpoint.

Rate of Change in Hair Growth: The rate of change in hair growth at 8, 16 and 26 weeks will be analyzed in the same manner as the primary endpoint.

Independent Physician's Global Assessment (iPGA): The percentage of participants with each score will be summarized by treatment group and by week. The active cap groups will be compared to the Sham group using Cochran-Mantel Haenszel (CMH) chi-squared method for detecting shifts in distribution of answers. The modified RIDIT scores will be used to take into account the ordered nature of the categorical responses. An example of SAS code for this analysis is as follows:

```
IF ARM IN ('SHAM', 'CAP101');
PROC FREQ;
```

TABLE ARM*(iPGA08 iPGA16 iPGA26) /CMH SCORE=MODRIDIT; RUN;

Site Physician's Global Assessment (sPGA): The site investigator will assess over hair growth using the PGA scores at weeks 8, 16 and 26. These outcomes will be summarized and analysed in the same manner as the iPGA, above.

Subjective Scalp Hair Growth Score (SHG): The percentage of participants with each score in for each question will be summarized by week and by treatment group. The active cap groups will be compared to the Sham group using Cochran-Mantel Haenszel (CMH) chi-squared method for detecting shifts in distribution of answers. The modified RIDIT scores will be used to take into account the ordered nature of the categorical responses. An example of SAS code for this analysis is as follows:

```
IF ARM IN ('SHAM', 'CAP101');
PROC FREQ;
TABLE ARM*(SHG1 SHG2 SHG3 SHG4 SHG5A SHG5B SHG5C)
/CMH SCORE=MODRIDIT;
RUN;
```

Hair Specific Skindex-29 Quality of Life Questionnaire (HSSQOL): The sum of scores for overall will be summarized by treatment group for each visit. These outcomes will be summarized and analysed in the same manner as the SHG above.

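### SAP 8.2 extends the primary endpoint's superiority rule to every secondary outcome, with no error control across endpoints and visits and no requirement that the cap first meets the primary

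*Combined protocol and SAP*

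**What the plan says.** SAP 8.2 sets out a process for the primary outcome, the week-16 change in hair count. The null hypothesis is rejected for a cap "if the Dunnett's corrected p-value for the contrast ≤ 0.05", and superiority is "demonstrated if the significant difference is in favor of the active cap". The multiplicity control is: "Comparisons will be adjusted for multiple comparisons to the same Sham group using Dunnett's correction". The section then turns to the other outcomes: "Secondary outcomes will the same hypotheses testing process as the primary outcome", with only the statistical method varying by endpoint type.

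SAP 8 sets the default that "statistical significance will be determined using p ≤ 0.05" unless stated otherwise. SAP 10.2 lists the secondary analyses. Hair count at weeks 8 and 26 and rate of change at three visits follow the primary's method. The two physician assessments (iPGA and sPGA), the SHG items and the overall quality-of-life score (HSSQOL) use the CMH test. The SHG example code tests seven items separately: "TABLE ARM*(SHG1 SHG2 SHG3 SHG4 SHG5A SHG5B SHG5C".

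SAP 8, 8.2 and 10.2 contain no testing order, no gate on the primary, no alpha split and no label such as nominal, supportive or exploratory. Protocol 5.2 promises only an adjustment for comparing several caps with one sham.

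**The concern.** Dunnett's correction deals with three caps sharing one sham arm within a single endpoint at a single visit. It does nothing about the number of endpoints and visits. Because SAP 8.2 carries the whole process over to the secondaries, the plan's own rule can be met separately on each of them, whatever happened on the primary. A cap with no hair-count benefit at week 16 could be called superior to sham on one SHG item at week 8.

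At stake is how far any superiority statement based on a secondary can be trusted. This is a stated rule that produces such statements, not merely a missing detail.

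**Working it through.** **The plan's own figure.** SAP 5 states: "Assumptions are 15 hair count difference between treatments, standard deviation (SD)=20, 10% drop-out rate, 5% alpha level, 90% power and 2-sided t-test", and concludes that "the study requires a minimum of 40 evaluable participants per arm". By the normal approximation, n = 2 × (1.960 + 1.282)² × 20² / 15² = 37.4, so 38 per arm. The exact t calculation gives 39, with 91.2% power at 40. The stated 40 is reproduced. It concerns one hair-count contrast at unadjusted 5%. The documents give no count of secondary tests and no error rate across endpoints.

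**Count of families** (one endpoint at one visit, three caps against sham), from SAP 8 and 10.2:

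| Endpoint | Visits × items | Families | Method in SAP 10.2 |
|---|---|---|---|
| Hair count | 2 | 2 | as primary (Dunnett) |
| Rate of change | 3 | 3 | as primary (Dunnett) |
| iPGA | 3 | 3 | CMH, one cap against sham |
| sPGA | 3 | 3 | CMH, as iPGA |
| SHG | 3 × 7 | 21 | CMH, one cap against sham |
| HSSQOL overall | 3 | 3 | CMH, as SHG |

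Total: 2 + 3 + 3 + 3 + 21 + 3 = 35 families and 35 × 3 = 105 contrasts. Not counted are the per-protocol repeats (SAP 6), the no-imputation repeats (SAP 8.1) and optional subgroups (SAP 8.4).

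**Error within one family.** With 40 per arm, df = 160 − 4 = 156 and the simulated two-sided Dunnett critical value is 2.37. With all caps ineffective, 5.0% of families have some rejection and 2.5% have one favouring a cap. The 2.5% is also the primary's false-superiority rate.

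**Expected number.** In either direction: 35 × 0.05 = 1.75. Favouring a cap: 35 × 0.02515 = 0.88.

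**At least one false superiority finding across the 35.** If independent, 1 − (1 − 0.02515)³⁵ = 0.59. Otherwise I simulated three caps and a shared sham (normal approximation, critical value 2.349) with an assumed common correlation between families. The last column leaves the 30 CMH families unadjusted for three caps, as the example code in SAP 10.2 has them. Each of those then has 12.4% error, 6.2% in the cap's favour.

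| Assumed correlation | All 35 held at 5% | 30 CMH families unadjusted |
|---|---|---|
| 0 | 59% | 87% |
| 0.3 | 40% | 64% |
| 0.5 | 29% | 49% |
| 0.7 | 20% | 35% |
| 0.9 | 10% | 19% |

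A block structure is closer to these endpoints: hair count with rate, the two physician assessments, SHG, and quality of life. With assumed correlations of 0.6-0.8 within blocks and 0.2-0.3 between them, the chance is 24-34% with every family held at 5%.

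**The case against.** The strongest reply is that the primary is protected: one endpoint, one visit, Dunnett across caps, and the trial is powered on it. That stands. A reader might infer that the trial's main conclusion is compromised, and the documents do not support that.

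A second reply is that the superiority sentence sits in the primary's paragraph with a hair-count example, so carrying it to the secondaries rests on a sentence that lacks its verb. That is fair, but the sentence speaks of the same testing process, and nothing elsewhere restricts it.

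Third, the endpoints are strongly related. Week-16 rate of change is the primary change divided by baseline, carried-forward values link the visits, iPGA and sPGA grade the same photographs, and 21 of the 35 families come from one questionnaire. This also stands. A reader might infer that a false superiority finding is likely, but the chance passes one half only near independence if each family is held at 5%. A reader might also take 1.75 as the number of false superiority findings. That figure counts both directions, and about half favour a cap.

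Fourth, 35 is a count by inference. The protocol names SSHG (the SAP's SHG) as one endpoint, and the SAP table list has no rate-of-change table. The item-by-item code and the SHG tables for each week make the count reasonable. Nor does SAP 10.2 hold all 35 families at 5%: only five have Dunnett in their stated method. That departure raises the error rate.

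**Conclusion.** The point holds. As written, SAP 8.2 lets any secondary outcome at any visit meet the superiority rule, without control across endpoints and without success on the primary. With all caps ineffective and each family held at 5%, the chance of at least one false superiority finding is roughly 20-40% at correlations of 0.3-0.7, and about four times the primary's 2.5% even at 0.9. The correlations are assumptions, since the documents give none, and the figures rest on the count of 35. Pairwise CMH without a cap adjustment raises them. The per-protocol and no-imputation repeats add further looks, which are not quantified here and overlap heavily with the main analysis. Since the primary is unaffected, this is a change that should be made, not a fatal flaw.

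**What to change.** Replace the sentence on secondary outcomes in SAP 8.2 with: *Secondary endpoints are supportive; their p-values are nominal, and the superiority rule applies to the primary endpoint only.*

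If the sponsor wants formal secondary claims, it should prespecify, before unblinding, a short fixed sequence of its own choosing. The sequence should be open only to caps that meet the primary, run in one named population, and use a procedure shown to hold 5% across caps and endpoints. Naming the population means reconciling protocol 5.3, which assigns secondary efficacy to the per-protocol set, with SAP 6, which adds per-protocol to the main analysis. Following the Dunnett criterion (about 0.019 per contrast) with steps at 0.05/3 = 0.0167 per cap should not be assumed to hold 5% without a check.

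The nominal label needs no new data, procedures or sample size. Its cost is fewer formal claims from secondaries.

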8.3. Covariates

Demographic and baseline characteristics, such, but not limited to age, gender, race and baseline hair count, will be consider as covariates in the ANCOVA. Any covariate that significantly accounts for variability (p<0.10) in the ANOVA model or Chi-Square test will be retained for the hypothesis testing.

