2.2 Study Design Overview

This study is designed as a prospective, randomized, controlled, double-blind, four-arm study. Up to 4 clinical sites will enroll up to 200 participants over an approximate 7-month duration. Eligible participants with AGA meeting inclusion and exclusion criteria will be enrolled and randomized to one of four study arms.

```
      Study Arm 1: Active REVIAN 101 (_____ mW/cm^2 of 625 nm and 660 nm)

      Study Arm 2: Active REVIAN 102 (_____ mW/cm^2 of 425 nm)

      Study Arm 3: Active REVIAN 103 (____ mW/cm^2 of 425 nm + ____ mW/cm2 of 625 nm and 660 nm)

      Study Arm 4: Non-Active REVIAN (SHAM) Cap 100
```

The outcome measures in this study will include the following:

- Quantitative Scalp Hair Growth (Macrophotography of 1-cm² area of interest)
- Subjective Scalp Hair Growth (SSHG) score
- Physician's Global Assessment (PGA) score
- Hair Specific Skindex-29 Quality of Life Score Questionnaire

All participants will be asked to complete self-administering scalp hair growth and life quality questionnaires at each follow-up visit. Investigators will be required to complete global assessments of scalp hair growth for each enrolled participant at each follow-up visit.

Macrophotography evaluations will be performed at baseline, 8-, 16-, and 26 weeks for all participants. Global photographs of superior and vertex scalp will be taken by the PI to be assessed by a blinded reviewer once all photos have been captured for each participant per visit.

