3.4.3 Randomization of Treatment Device

All participants will be randomized to one of four study arms. The randomization will be a block design, stratified across the sites and maintained by the local Study Sponsor. Each site will be blinded to the randomization code and will only receive a pre-assigned code to use for each participant at time of enrollment. The code will be pre-assigned to one of the four caps below:

Study Arm 1: Active REVIAN Cap 101Study Arm 2: Active REVIAN Cap 102Study Arm 3: Active REVIAN Cap 103Study Arm 4: Non-Active REVIAN (SHAM) Cap 100

3.4.4 Week 1 Phone Call – (7±3 Days), Visit 3

- Concomitant medication usage
- Adverse Events
- Compliance Follow-up

3.4.5 Week 8 Follow-Up Visit – (56±5 Days), Visit 4

- Subjective Scalp Hair Growth (SSHG) Score
- Physician's Global Assessment (PGA) Score
- Hair Specific Skindex-29 Quality of Life Questionnaire
- Global Photography Image of Two Views (superior and vertex scalp)
- Shave and Tattoo Scalp
- Hair Count Macrophotography (1cm² Area)
- Concomitant medication usage
- Adverse Events
- Compliance Follow-up

3.4.6 Week 16 Follow-Up Visit – (112±10 Days), Visit 5

- Subjective Scalp Hair Growth (SSHG) Score
- Physician's Global Assessment (PGA) Score
- Hair Specific Skindex-29 Quality of Life Score Questionnaire
- Global Photography Image of Two Views (superior and vertex scalp)
- Shave and Tattoo Scalp
- Hair Count Macrophotography (1cm² Area)
- Concomitant medication usage
- Adverse Events
- Compliance Follow up

3.4.7 Week 26 Follow-Up Visit – (182±10 Days), Visit 6

- Physical Exam (including vital signs)
- Subjective Scalp Hair Growth (SSHG) Score:
- Physician's Global Assessment (PGA) Score:
- Hair Specific Skindex-29 Quality of Life Score Questionnaire
- Global Photography Image of Two Views (superior and vertex scalp)
- Shave and Tattoo Scalp
- Hair Count Macrophotography (1cm² Area)
- Concomitant medication usage
- Adverse Events
- Compliance Follow up
- Exit/Termination Form

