5.2 Study Analysis, Sample Size and Pooling of Data

Study Analysis:

The primary efficacy analysis of this study is to compare the mean change in hair count change from baseline to 16-weeks following the initial application at baseline of REVIAN to the SHAM. This will be performed using mixed effects analysis of covariance (ANCOVA) where baseline characteristics and demographics may be considered as covariates. Comparison between active groups will not be tested for statistical significance as the study is not powered for these comparisons. Instead, each active will be compared to the SHAM individually. Details on adjustments for multiple testing to a single SHAM will be provided in a statistical analysis plan.

Power Calculation, Sample Size:

Prior hair growth studies, regardless of potential efficacy of the SHAM device, showed the delta between active treatments and control treatments was consistently at around 15-22 hairs/cm² which appears to be the expected level of improvement. It is estimated that participants in the active group will have greater than 15 hairs/cm² by 16-weeks. The study design is a parallel arm study of superiority of PhotonMD devices to SHAM with a minimum of 40 participants per arm. Assumptions are 15 hair difference between treatments, standard deviation (SD)=20, 10% dropout rate, 5% alpha level, 90% power and 2-sided t-test.

The study will accrue a total of 200 participants (50 per each Active Study Arm and 50 control participants) to make sure, after lost to follow-up, that there is a minimum of 160 evaluable (40 per arm) participants.

Pooling of Data:

The clinical study will be conducted under a common protocol for each of 3 investigational sites with the intention of pooling the data over all sites for analysis. Every effort will be made to promote consistency in study execution at each investigational site.

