3. STUDY DESIGN

This study is designed as a prospective, randomized, controlled, double-blind, four-arm study. Up to 3 clinical sites will enroll up to 200 participants over an approximate 6-month duration. Eligible participants with AGA meeting all inclusion and exclusion criteria will be enrolled and randomized to one of four study arms in a 1:1:1:1 ratio:

- Arm 1: Active *REVIAN* 101 (___mW/cm² of 625 nm and 660 nm)
- Arm 2: Active *REVIAN* 102 (____mW/cm² of 425 nm)
- Arm 3: Active *REVIAN* 103 (____mW/cm² of 425 nm + ___mW/cm2 of 625 nm and 660 nm)
- Arm 4: Non-Active *REVIAN* Cap 100 (SHAM)

Male and female participants will be randomized from separate randomization schedules to ensure balance among treatment arms in each gender.

All data except for Global Assessment Photography and Macrophotography will be captured in an electronic clinical report form (eCRF). Global Assessment Photography and Macrophotography data will be imported from external vendor. Demographic, baseline characteristics, efficacy and safety data will be collected at regularly scheduled visits according to the planned schedule of procedures (Table 1).

Screening procedures will be performed at Visit 1.

Participants who are eligible to enroll will return within 7 days for Visit 2 to obtain baseline data and to be randomized to one of the treatment arms. The first treatment will be performed in the clinic on Visit 2.

Visit 3 will occur approximately 7 days later via telephone interviews to assess treatment compliance, to report use of concomitant medications and to report any adverse events.

Visits 4 and 5 will occur approximately 8 and 16 weeks, respectively, after Visit 1. Participants will return to the investigation centers for efficacy assessments and questionnaires.

The final visit (Visit 6) will occur approximately 10 weeks after Visit 5. Participants will undergo a final assessment of efficacy and safety at Visit 6. Participants will return the caps at Visit 6. If there are no adverse events requiring follow-up, participants will not need to return for any follow up assessments.

Any participant who competes the Week 16 efficacy assessments (at Visit 5) will be considered a completer.

Visit 1	Visit 2	Visit 3	Visit 4	Visit 5	Visit 6
Screening (Day -7)	Baseline (Day 0)	Phone Call (7 ±3 Days)	Week 8 ^{1,2} (56 ±5 Days)	Week 16 ^{1,2} (112 ±10 Days)	Week 26 ^{1,2} (182 ±10 Days)
X	Х				
X					
Х					
X					
X	Х				
X	Х				
	Х				Х
	Х				
	Х		Х3	X ³	X ³
	Х		Х	Х	Х

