10. EFFICACY ANALYSES

10.1. Primary Endpoint

The primary efficacy endpoint is the change from baseline in hair count, over a pre-specified 1 cm² area of scalp after 16 weeks of treatment (CFB_HC16).

As specified in Section 9.2, each active cap will be compared to the same Sham treatment using 1 degree of freedom contrasts in an analysis of covariance (ANCOVA). Analyses will be adjusted for multiple comparisons using Dunnett's correction. An example of SAS code to be used for the primary analysis is as follows:

PROC MIXED; CLASS SITE ARM; MODEL CFB_HC16 = SITE ARM SITE*ARM <covariates>; LSMEANS ARM /ADJUST=DUNNETT DIFF=CONTROL('SHAM'); RUN;

If the SITE*ARM interaction is not significant (p>0.05), this interaction will be dropped from the subsequent model. SITE will remain in the model if it significantly attributes to variability of the outcome. All subsequent analyses of secondary endpoints will retain the same factors and covariates as the primary outcome analysis.

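### The primary ANCOVA fixes none of site, sex or baseline hair count, so the final model is known only after week-16 outcomes by arm have been analysed

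*Combined protocol and SAP*

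**What the plan says.** Two factors enter the randomisation. Protocol 3.4.3 states: "The randomization will be a block design, stratified across the sites". SAP 3 adds: "Male and female participants will be randomized from separate randomization schedules to ensure balance among treatment arms in each gender". Baseline hair count is available for every participant, since protocol 2.2 states: "Macrophotography evaluations will be performed at baseline, 8-, 16-, and 26 weeks for all participants".

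The analysis text treats all three as optional:

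- **Protocol 5.2** describes a mixed effects ANCOVA "where baseline characteristics and demographics may be considered as covariates".
- **SAP 8.3** makes sex and baseline count examples in an open list: characteristics "such, but not limited to age, gender, race and baseline hair count, will be consider as covariates in the ANCOVA". The retention rule follows: "Any covariate that significantly accounts for variability (p<0.10) in the ANOVA model or Chi-Square test will be retained for the hypothesis testing".
- **SAP 10.1** starts from site, arm, their interaction and unnamed covariates, and then prunes. On the interaction: "If the SITE*ARM interaction is not significant (p>0.05), this interaction will be dropped from the subsequent model". On site: "SITE will remain in the model if it significantly attributes to variability of the outcome". This rule gives no threshold of its own.
- **SAP 8.5** also has a dropping rule for the case of no interaction. It most naturally refers to the interaction, but it can be read as dropping site itself.

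SAP 10.1 passes the selected terms on to the secondary analyses. The review before unblinding in SAP 8.6 concerns data queries. No section requires model selection to be done blind to arm.

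**The concern.** A primary model should be identifiable before outcomes are seen. Here the thresholds are partly stated but the resulting model is not. Each cap's estimate depends on which terms pass a p-value in the same data used to test the cap. Two of the terms at risk are randomisation strata, and the third is a baseline measurement of the outcome variable.

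The quantity estimated can also change. If the interaction is kept, the planned `LSMEANS ARM` statement weights sites equally instead of by their size.

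The choice carries over to the other ANCOVA endpoints: hair count at weeks 8 and 26, and rate of change. It does not reach iPGA, sPGA, the subjective growth score or Skindex-29, because the CMH code in SAP 10.2 contains no site or covariate.

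**Working it through.** **The plan's own sample size.** SAP 5 uses a difference of 15, SD 20, two-sided 5% alpha and 90% power. The normal approximation gives n = 2(1.960 + 1.282)² × 20²/15² = 37.4, so 38 per arm. The noncentral t gives 39. The stated 40 is reproduced. That calculation has no covariates, so it does not depend on the model choice.

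**Can the rule be carried out as written?** Not without further choices. The candidate list is open. A chi-square test is named although the outcome is continuous. The site threshold could be 0.05 (the SAP 8 default) or 0.10 (if site counts as a covariate). The degree of site imbalance that blocks the interaction analysis in SAP 8.5 is undefined, and no order of steps is given.

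**Simulation.** From the documents: 200 participants, 50 per arm, 60% men, SD 20, three Dunnett contrasts against sham (cut-off 2.366 on 190 df). Assumed:

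- permuted blocks of 4 within site by sex, and no true interaction;
- four named candidates (age, sex, race, baseline count) screened together at p<0.10 in the model with arm, site and interaction;
- interaction kept if p≤0.05; otherwise site kept if p≤0.05;
- shares of variance explained by site, sex and baseline count, as in the table.

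The comparator is ARM + SITE + SEX + baseline count, fitted to the same data. Each setting had 60,000 null trials and 20,000 trials with a 15-hair effect. Site sizes were 52/52/48/48 or 68/68/64, because the documents give both three and four sites. Entries are SAP rule minus fixed model, in percentage points.

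| Site/sex/baseline share | Excess error, 4 sites | Excess error, 3 sites | Per-cap power, 4 sites | Per-cap power, 3 sites |
|---|---|---|---|---|
| 0/0/0% | +0.26 | +0.23 | +0.17 | +0.26 |
| 1/1/2% | +0.24 | +0.22 | -0.06 | -0.02 |
| 2/2/5% | +0.12 | +0.14 | -0.08 | -0.03 |
| 5/5/10% | +0.13 | +0.13 | +0.02 | +0.02 |

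In absolute terms, family-wise error is 5.1 to 5.2% against 4.9 to 5.0%. The mean estimate is 15.0. At 2/2/5% the rule omits site in 53 to 58% of trials, sex in 34% and baseline count in 7%. Other simulations with near-equal sites put the rule between 5.0 and 5.4%, against 4.9 to 5.0% for the fixed model.

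One of these (4,000 runs per scenario; baseline correlation 0 to 0.5, sex effect 0 to 8 hairs, site steps 0 to 5 hairs) ended in 20 to 39 different final models per scenario. The most frequent model occurred in only 23 to 70% of trials. If the most favourable of four models (two readings of the SAP, the fixed model, no adjustment) could be chosen afterwards, error was 6.2 to 8.6%. That bounds the effect of discretion and is not a forecast: two of the four lie outside the SAP rule.

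**Unequal sites.** Protocol 2.5 allows 100 participants at one site. At 2/2/5%, splits of 80/60/40/20 and 100/52/28/20 give error of 5.4 to 5.5% against 5.0 to 5.1%, and power lower by 0.5 to 0.9 points. A separate run at 100/52/28/20 gave 5.7% against 5.2%, with power about 0.7 points lower.

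The interaction is kept by chance in about 5% of trials. A site with 20 of 200 participants (10%) then receives 1/4 = 25% of the weight. For 80/60/40/20 (20/15/10/5 per arm), the variance multiplier is (1/16)(1/20 + 1/15 + 1/10 + 1/5)/(1/50) = 1.30, so the standard error rises about 14% before any fall in residual variance. The simulated increase over the two splits is 11 to 16%.

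**Long candidate list.** With 13 candidates (the 4 named plus 9 other collected baseline variables), error is 5.8% against 5.1% with near-equal sites and 6.0% against 5.1% at 100/52/28/20.

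**Cost of fixing the model.** With arm alone, SE = 20√(2/50) = 4.0, and 15/4.0 - 2.366 = 1.38, giving about 92% power (noncentral t: 91.6%). If the three terms explain 9% of variance, SE = 4.0√0.91 = 3.82, giving about 94%. If they explain nothing, the fixed model has 91.3 to 91.4% against 91.6% for the SAP rule.

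**The case against.** The strongest reply is that the harm is negligible. Followed mechanically, the stated thresholds form a largely prespecified algorithm. One simulation at 2/2/5% found error of 5.02% against 4.98% and power of 93.9% against 94.0%. The rule usually keeps what matters: baseline count is omitted in only 7% of trials there. The 94% against 91.6% contrast with arm alone is therefore not a gain over the SAP. All of this stands.

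It is also true that no selection step uses the treatment p-value. The F-tests for interaction, site and covariates do not change if arm labels are permuted, so they could be run on masked codes. The SAP does not require this, though, and masking would settle neither the open list, nor the site threshold, nor the change of weighting when the interaction is kept.

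The upper-range figures are rightly discounted. SAP 8.5 may exclude the interaction analysis when sites are very unequal, and the SAP does not say that 13 variables would be screened. Block size, crossed strata and screening order are assumptions too. The defect itself depends on none of them.

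**Conclusion.** The concern holds. No section fixes site, sex or baseline hair count in the final primary model, and the interaction step needs week-16 outcomes grouped by arm. With near-equal sites and the four named candidates, the excess family-wise error is at most about 0.4 points, the power difference is within about 0.3 points either way, and there is no bias in the mean estimate. Larger figures (error up to 6.0%, power loss up to 0.9 points) need unequal sites or a long candidate list. All these figures rest on assumed variance shares, site sizes and order of steps.

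The case for change is therefore identifiability, not rescue from a large error: one prespecified estimate per cap, at nominal error, that respects the randomisation strata. It should be changed, but it does not threaten the trial's conclusions.

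**What to change.** In SAP 10.1, fix the primary model as change in week-16 hair count = ARM + SITE + SEX + baseline hair count. Keep all terms whatever their p-values, with Dunnett contrasts against sham. Delete the p<0.10 rule in SAP 8.3 and the dropping rules in 8.5 and 10.1. Report the site-by-arm interaction as a supportive consistency check that cannot alter the primary model. Use the same fixed terms for hair count at weeks 8 and 26 and for rate of change. Name any further covariate, such as age or race, before unblinding, and align the wording of protocol 5.2.

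The cost is rewording and a few lines of SAS, with no new data. The added terms use 4 degrees of freedom with three sites (2 + 1 + 1) or 5 with four (3 + 1 + 1), out of 200 - 4 = 196. The worst case is about 0.3 points of power, if none of the three terms predicts the outcome.
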